## Introduction

The poor prognosis of triple-negative breast cancer (TNBC) results from a lack of available targeted treatment options coupled with the aggressive biological behavior of this subtype, which is associated with a high risk of early recurrence, particularly visceral metastasis. However, chemotherapy is the only adjuvant treatment option for patients with early-stage TNBC. Effective maintenance therapies to reduce the risk of relapse and death are needed.

Chemotherapy using lower dosage and higher frequency is thought to exert its anticancer activity by targeting 2 mechanisms of metastasis: angiogenesis and immune escape. Therefore, low-dose chemotherapy might prevent TNBC from metastasizing.

Capecitabine, an orally administered chemotherapeutic drug used widely in the treatment of metastatic breast cancer, is a potential candidate therapy for low-dose administration as maintenance to prevent recurrence.

Several previous clinical trials added high-dose capecitabine to standard breast cancer adjuvant chemotherapy regimens and have reported conflicting results, In this study, was designed to evaluate the effect of low-dose capecitabine maintenance therapy after completion of standard adjuvant treatment on disease-free and overall survival in women with early-stage TNBC.

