## Study design

This study is a randomized, phase 2 clinical trial study and will be enrolled at clinical oncology department, Faculty of medicine, Beni-Suef University .

The study will investigate the effect of low dose and high frequency of receiving capecitabine as maintenance therapy in patients with low risk triple negative breast cancer.

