## Methods

Eligible patients will randomly open label assigned in a 1:1 ratio to receive either low-dose capecitabine maintenance (intervention group) which is newly diagnostic to be planned to receive capecitabine after finishing the standard adjuvant treatment or observation (control group) within 4 weeks after completion of standard adjuvant chemotherapy.

The capecitabine maintenance group will receive oral capecitabine at 650 mg/m^2, twice daily continuously for 1 year.

Total follow up of the study is 2 years, one year for drug receiving with monthly follow up for adverse effect and the other year for every 3 months follow up to assess DFS and OS.

Collection of capecitabine dose will receive and adverse events will be assessed monthly during capecitabine maintenance in the capecitabine group. In both groups, physical examination, assessment of menopausal status, breast ultrasound, and abdominal ultrasound were performed every 3 months during 2 years of follow up; mammography and chest x-ray were performed yearly. Patients who have not experienced recurrence or death at the time of data analysis will be censored as alive and event-free at the date of last follow-up.

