#### Sample size

Sample size was calculated based on online openepi calculator. We calculated the required sample size to detect a statistically significant difference in AE rates between groups using a two-sided chi-square test. Therefore, our planned enrollment of 80 patients (40 per group) is sufficient to detect clinically meaningful differences in treatment-emergent adverse events.

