#### Study end points

The primary end point of the study is to assess the adverse effects of the Capecitabine after 6 months after starting treatment.

Secondary end points will include

1. Disease-free survival, defined as the time from randomization to the first occurrence of the following events: local relapse, distant metastasis or contralateral breast cancer.
2. overall survival (the time from randomization to death from any cause).
3. Adverse events were assessed and graded according to the National Cancer Institute's Common Terminology Criteria for Adverse Events version 4.0. Hand-foot syndrome (a common adverse effect of the fluoropyrimidine chemotherapy agent capecitabine) events will graded from 1 to 3.

Statistical Analysis:

For statistical analysis, all data will recorded and analyzed .The p-value reports will two tailed and an alpha level of 0.05 was used to assess statistical significance. Time-to-event curves will be described using the Kaplan-Meier method. A Cox proportional hazards model will be used to estimate and test the treatment effect. Analysis of the interaction between treatment effects and selected subgroups will conducted using a  $\chi^2$  test for heterogeneity and described with forest plots. Q statistics and I values will be used to assess the potential heterogeneity of trial-specific Disease-Free Survival. The data will be coded and entered using: the statistical package for social science version 22 (SPSS v 22). For descriptive analysis of the result, the data will be summarized using (minimum, maximum, mean and standard deviation) for quantitative data and the frequency distribution for qualitative data. Student t- test: for comparison between means of two groups of quantitative variables. Paired sample t-test will be used for comparison between means of paired quantitative variables. Chi square test: for comparison between two groups of categorical data or frequency of events.

P: The probability/significance value

P value  $\geq 0.05$ : Not significant

P value  $< 0.05$ : Significant

The Correlation coefficient (r): A positive correlation coefficient means that as the value of one variable increases, the value of the other variable increases; as one decreases the other decreases. A negative correlation coefficient indicates that as one variable increases, the other decreases, and vice-versa. Graphic presentations in this study will done by: means of "Microsoft excel version 2007".

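### Does an Introduction that names survival as the design purpose undermine a trial sized and ranked on adverse events?

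*Combined protocol and SAP*

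**What the plan says.** The Introduction closes by saying that the study "was designed to evaluate the effect of low-dose capecitabine maintenance therapy after completion of standard adjuvant treatment on disease-free and overall survival". Safety is not mentioned in that sentence. The Aim of the work section covers both efficacy and adverse events, without ranking them.

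The operative sections are more specific:

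- Study end points: "The primary end point of the study is to assess the adverse effects of the Capecitabine after 6 months after starting treatment". DFS and OS then appear in the list that opens "Secondary end points will include".
- Sample size: "We calculated the required sample size to detect a statistically significant difference in AE rates between groups", by a two-sided chi-square test. The stated conclusion is that 80 patients (40 per group) "is sufficient to detect clinically meaningful differences in treatment-emergent adverse events". No time point is given there, and nothing is said about DFS or OS.
- Methods: "Total follow up of the study is 2 years", with DFS and OS assessed over that period.
- Statistical Analysis (within Study end points): Kaplan-Meier curves, and "A Cox proportional hazards model will be used to estimate and test the treatment effect". A two-tailed 0.05 threshold applies generally, with two labels, significant and not significant. The Cox endpoints are not named, but DFS and OS are the only time-to-event endpoints. Confidence intervals are not mentioned, and no p-value is marked as exploratory.

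**The concern.** Read in order, the document first promises an answer on survival and then builds a trial around adverse events. The Cox test nevertheless falls under the same two-label rule as every other test. If DFS gave P≥0.05, a reader who remembered only the Introduction could take that as the answer to the trial's question and conclude that maintenance capecitabine does not work. With 80 patients and 2 years of follow-up, such a result would say very little either way. At stake is a false negative reading of efficacy that the design could never have supported.

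**Working it through.** **The plan's own figure.** The 80 patients cannot be reproduced, because no adverse-event rates, difference or power are stated. The number is plausible for its stated purpose. Under an uncorrected two-sided chi-square test at 0.05 with 80% power, assumed rates of 20% versus 50% need 39 per arm, and 1% versus 20% need 40 per arm.

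**Events needed for DFS** (1:1 allocation, two-sided 0.05, 80% power; the HRs are assumptions). Events = 4(1.96 + 0.842)² / (ln HR)².

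- HR 0.5: 65.3, so 66 events. This is below 80 but would require most patients to relapse.
- HR 0.6: 120.3, so 121 events. This exceeds the 80 patients.
- If all 80 patients had an event, power at HR 0.6 would be Φ(0.511 × 8.944 / 2 − 1.96) = 63%.

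**Events expected.** The documents give no DFS rate. The Study design section describes "maintenance therapy in patients with low risk triple negative breast cancer", while the Introduction stresses a high risk of early recurrence, so a wide range is used: control 2-year DFS S₀ from 60% to 95%, HR 0.5 or 0.7, and everyone followed for 2 years.

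Expected events d = 40(1 − S₀) + 40(1 − S₀^HR). Power = Φ(|ln HR| × √d / 2 − 1.96).

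| S₀ | HR 0.5: events, power | HR 0.7: events, power |
|---|---|---|
| 0.60 | 25.0, 41% | 28.0, 15% |
| 0.75 | 15.4, 27% | 17.3, 11% |
| 0.90 | 6.1, 13% | 6.8, 7% |
| 0.95 | 3.0, 9% | 3.4, 5% |

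Worked line: S₀ = 0.60, HR 0.5 gives 40 × 0.40 + 40 × (1 − 0.775) = 25.0 events, and Φ(0.693 × 5.0 / 2 − 1.96) = 41%. Log-rank simulation (20,000 trials per cell, exponential DFS) gives 4–40% over the same grid. The formula is only approximate at the lowest counts. Dropout would lower all these figures.

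**What would be labelled significant.** With events split roughly evenly, the largest observed HR reaching P<0.05 is exp(−3.92 / √d): 0.48 at 28 events, 0.36 at 15 and 0.20 at 6. An observed HR of 0.50 needs d = (3.92 / 0.693)² = 32.0 events, which is 40% of the 80 patients. At a true HR of 0.5 that means S₀ + √S₀ = 2 − 32/40 = 1.2, so S₀ is about 0.50, outside the assumed range.

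Event counts vary around their expectation, so this is not a certainty. At S₀ = 0.60 and HR 0.7, about 20% of simulated trials had 32 or more events. Among trials at S₀ = 0.60 with an observed HR near 0.50, about 4–9% were significant; at 0.75 and 0.90, none were.

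**Does this show a fault in the plan?** Setting the sections side by side:

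- The Introduction gives a purpose but does not call DFS or OS primary and claims no power for them.
- The Aim of the work section covers both efficacy and safety, so it is compatible with either emphasis.
- Study end points ranks them, and Sample size follows that ranking.
- The 0.05 rule attaches a label to a p-value. It does not say that a non-significant result means no efficacy.

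The calculation therefore measures how little a secondary endpoint can show. It does not measure any harm caused by the Introduction's wording.

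**The case for a change.** The strongest case for a change is that the sentence is not mere background. It states what this study was designed to do, and the design does not match. The analysis section then gives a two-way verdict with no caveat, no interval and no ordering of tests. Naming the Cox endpoints, reporting intervals and calling the p-values exploratory would cost a few lines and no patients. If DFS events are rare, an arm may have none: the chance is S₀⁴⁰ + S₀^(40·HR) minus their product, which is 7–13% at control DFS of 90% and 34–44% at 95%. The hazard ratio could not then be estimated.

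Much of this stands as description. The mismatch is in the current text, the Aim of the work section does not settle it by itself, and a non-significant DFS result would be uninformative. What does not follow is a fault in the plan. The ranking is explicit where a reader would look for it. The Cox model is already meant to estimate as well as test, so an interval can be calculated from the same fit. At the event counts above it would be visibly wide, with the HR divided and multiplied by exp(3.92 / √d): about 2.1 at 28 events, 2.8 at 15 and 5.0 at 6. Kaplan-Meier curves are planned and remain available if an arm has no events. A secondary endpoint in an 80-patient phase 2 trial would be read cautiously with or without the word exploratory. The documents also do not show that the Introduction, rather than the ranking, departs from the sponsor's intent, so instructing a rewording would mean choosing a side.

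**Conclusion.** The inconsistency is a minor slip of wording in one Introduction sentence that is itself grammatically incomplete. Correcting it would change no endpoint, sample size, model or p-value. The absent intervals and exploratory label are gaps that a competent analyst fills when reporting. Followed as written, the plan still gives a valid adverse-event comparison, a hazard ratio wherever both arms have events, and a correct p-value.

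The limitation is worth remembering when the results are read. On assumed control 2-year DFS of 60–95%, HR 0.5–0.7 and complete 2-year follow-up, power for DFS is about 5–41% on 3–28 expected events, and an observed halving of the hazard would almost always miss P<0.05. These figures rest on assumed rates, concern DFS only and would worsen with dropout. They describe the reach of a secondary endpoint for which the plan claims no power, and so give no reason to change it.

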## Aim of the work

The aim of work is to compare the efficacy and adverse events of low-dose capecitabine maintenance with observation following standard adjuvant treatment in patients with early-stage TNBC attend to oncology department, Beni- seuf university.

## Study design

This study is a randomized, phase 2 clinical trial study and will be enrolled at clinical oncology department, Faculty of medicine, Beni-Suef University .

The study will investigate the effect of low dose and high frequency of receiving capecitabine as maintenance therapy in patients with low risk triple negative breast cancer.

## Methods

Eligible patients will randomly open label assigned in a 1:1 ratio to receive either low-dose capecitabine maintenance (intervention group) which is newly diagnostic to be planned to receive capecitabine after finishing the standard adjuvant treatment or observation (control group) within 4 weeks after completion of standard adjuvant chemotherapy.

The capecitabine maintenance group will receive oral capecitabine at 650 mg/m^2, twice daily continuously for 1 year.

Total follow up of the study is 2 years, one year for drug receiving with monthly follow up for adverse effect and the other year for every 3 months follow up to assess DFS and OS.

Collection of capecitabine dose will receive and adverse events will be assessed monthly during capecitabine maintenance in the capecitabine group. In both groups, physical examination, assessment of menopausal status, breast ultrasound, and abdominal ultrasound were performed every 3 months during 2 years of follow up; mammography and chest x-ray were performed yearly. Patients who have not experienced recurrence or death at the time of data analysis will be censored as alive and event-free at the date of last follow-up.

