#### Inclusion criteria

Eligible trial participants will be women who have

1. Pathologically confirmed invasive breast ductal carcinoma
2. Hormone receptor negative (<1% positive cells by immunohistochemistry staining) and ERBB2 negative.
3. Participants had early-stage tumors that were stage T1b-3N0-3cM0, without positive supraclavicular or internal mammary lymph node involvement based on the American Joint Committee on Cancer (AJCC 2010, seventh edition) staging criteria.
4. They received standard treatments, including modified radical mastectomy or breast-conserving surgery, neo-/adjuvant chemotherapy, and radiotherapy according to institutional guidelines.

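### No adverse-event grade is taken at entry and treatment-emergent is undefined, so toxicity carried over from prior treatment cannot be separated from capecitabine toxicity in the primary endpoint

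*Combined protocol and SAP*

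**What the plan says.** - **Entry (Methods).** Patients are assigned to capecitabine or observation "within 4 weeks after completion of standard adjuvant chemotherapy". Under Inclusion criteria they have also had surgery, "neo-/adjuvant chemotherapy, and radiotherapy according to institutional guidelines".
- **Primary endpoint (Study end points).** "The primary end point of the study is to assess the adverse effects of the Capecitabine after 6 months after starting treatment". The text does not say whether this means status at month 6 or any event up to month 6, or which grades count.
- **What the trial is sized for (Sample size).** The enrolment of 80 (40 per group) is called sufficient for "clinically meaningful differences in treatment-emergent adverse events". The term is not defined anywhere.
- **AE schedule (Methods).** "adverse events will be assessed monthly during capecitabine maintenance in the capecitabine group". This is the only AE schedule given.
- **Visits common to both arms (Methods).** "In both groups, physical examination, assessment of menopausal status, breast ultrasound, and abdominal ultrasound were performed every 3 months". Mammography and chest x-ray are yearly. AE grading is not on the list.
- **Grading (Study end points).** Events are "graded according to the National Cancer Institute's Common Terminology Criteria for Adverse Events version 4.0", with no rule for a grade already present at entry.

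**The concern.** An endpoint that attributes adverse effects to capecitabine needs a reference point before the first dose. Patients arrive soon after chemotherapy, some of them perhaps also after recent radiotherapy, so some may still have symptoms that would be graded under CTCAE. The plan takes no grade at that moment. When such a symptom is seen at the first monthly visit, nothing in the data shows whether it is new.

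This goes beyond missing detail in the analysis section. An analyst can settle a definition later, but cannot reliably reconstruct a grade that nobody recorded before dosing began. At stake are the AE rate reported for capecitabine and the between-arm comparison on which the trial is sized.

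**Working it through.** **1. The plan's own figure.** The 80 patients can be neither reproduced nor refuted, because the documents give no AE rates, power or dropout. With 40 per arm, two-sided alpha 0.05 (both from the documents) and an assumed 80% power, the usual two-proportion formula without continuity correction gives the smallest detectable capecitabine rate as 36% against 10%, 49% against 20% and 61% against 30%. The trial is therefore credible only for differences of roughly 26 to 31 points, which leaves little room for distortion.

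**2. Carry-over model.** Let p0 and p1 be the true rates of new AEs under observation and capecitabine, and r the share of patients with carried-over toxicity, independent of new events. None of these is in the documents. If carry-over cannot be separated, an arm's any-AE rate becomes

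r + (1 − r)p.

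Power is computed by exact enumeration of the uncorrected Pearson chi-square test, 40 per arm, two-sided 0.05.

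**3. Scenario A: both arms graded alike, events counted cumulatively.** The difference becomes (1 − r)(p1 − p0). With assumed p0 = 10% and p1 = 40%:

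| r | Observation | Capecitabine | Difference (points) | Power |
|---|---|---|---|---|
| 0 | 10% | 40% | 30 | 0.90 |
| 5% | 14.5% | 43% | 28.5 | 0.82 |
| 10% | 19% | 46% | 27 | 0.74 |
| 20% | 28% | 52% | 24 | 0.61 |
| 40% | 46% | 64% | 18 | 0.39 |

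With assumed 20% versus 50%, power goes from 0.82 at r = 0 to 0.71 at r = 10% and 0.60 at r = 20%.

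**4. Scenario B: carry-over is recorded only in the capecitabine group.** This is the direction in which the Methods wording points. New events among controls are assumed still to come to notice, but not their carried-over symptoms. The difference becomes r + (1 − r)p1 − p0. With no true effect and an assumed 20% in both arms:

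| r | Observation | Capecitabine | Chance of a significant result |
|---|---|---|---|
| 0 | 20% | 20% | 5% |
| 10% | 20% | 28% | 13% |
| 20% | 20% | 36% | 36% |
| 30% | 20% | 44% | 64% |

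With an assumed 10% in both arms, the chances at r = 10% and 20% are 21% and 56%.

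**5. Scenario C: the endpoint is status at month 6.** Here r is the share of patients whose earlier toxicity persists to month 6. That share cannot exceed the share with toxicity at entry and may be much smaller. The formulas in steps 3 and 4 apply with that smaller r.

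**The case against.** The strongest case against the point has four parts.

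- **Intent.** The sample size section speaks of treatment-emergent events, so the authors apparently mean to exclude earlier toxicity. This is fair. The documents do not say that carried-over events will be counted, and a reader should not infer that they will. What stands is that neither the data nor the rule needed for the exclusion is provided.
- **Direction.** A reader might infer that carry-over must hide the capecitabine effect. The documents do not support this. Dilution requires grading both arms alike, and the only stated AE schedule is for the capecitabine group. On that wording the difference is inflated. Conversely, the stated aim and the sample size section both imply a between-group comparison, so symmetric recording remains possible.
- **Endpoint.** If only status at month 6 counts, toxicity that has resolved drops out. If only higher grades count, mild residual symptoms drop out. Both readings are open and both reduce the problem.
- **Size.** Every AE and carry-over rate above is assumed. At r = 5% the loss in scenario A is modest, from 0.90 to 0.82. To say that the trial cannot answer its primary question would go beyond the evidence.

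Randomisation does not dispose of the point. It balances carry-over between arms in expectation, but does not remove it from an any-AE proportion, and it offers no protection if the two arms are observed differently.

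**Conclusion.** The point holds in this form: entry is close to the end of chemotherapy, no AE grade is taken at entry, and treatment-emergent has no operational rule. As written, the plan cannot separate carried-over toxicity from capecitabine toxicity in its primary endpoint.

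Neither the direction nor the size of the bias can be fixed from the documents. Under the stated assumptions it ranges from a power loss of 0.08 (r = 5%) to 0.51 (r = 40%) when both arms are graded alike, to a false-positive chance of 13% to 64% (r = 10% to 30%) when carry-over is recorded only on capecitabine. It is smaller under a month-6 status endpoint if most carried-over toxicity resolves by then. The plan should be changed before enrolment, because the missing grade cannot be recovered afterwards.

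**What to change.** - **Methods, entry.** Grade AEs by CTCAE v4.0 in all patients at randomisation, before any capecitabine.
- **Methods, follow-up.** State the same AE assessment schedule for both arms. At the least, grade AEs in both arms at the 3-monthly visits that both already attend, and restrict the between-arm comparison to those common visits. Monthly grading on capecitabine can continue for description. A baseline grade without this step would leave controls with nothing to compare it with.
- **Study end points.** Define the primary endpoint as the proportion of patients with at least one AE that is new, or at least one grade worse than at entry, through month 6. Apply the rule identically in both arms, counting from randomisation, since controls have no treatment start date.

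The cost is one CTCAE form at entry, a little more form-filling at existing visits and a few sentences of text. It needs no additional patients, visits or procedures. The downside is small: a pre-existing symptom that capecitabine prolongs without worsening would not be counted.

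### The trial is sized to compare adverse event rates between groups, but adverse event assessment is scheduled only for the capecitabine group, and the 6-month window has no starting date in controls

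*Combined protocol and SAP*

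**What the plan says.** - **Aim of the work:** the trial is to "compare the efficacy and adverse events of low-dose capecitabine maintenance with observation".
- **Sample size:** "We calculated the required sample size to detect a statistically significant difference in AE rates between groups using a two-sided chi-square test". The section concludes that 40 patients per group is "sufficient to detect clinically meaningful differences in treatment-emergent adverse events".
- **Methods, AE collection:** "adverse events will be assessed monthly during capecitabine maintenance in the capecitabine group". Another sentence divides the 2-year follow-up into "one year for drug receiving with monthly follow up for adverse effect" and a second year of 3-monthly visits for DFS and OS.
- **Methods, common assessments:** "In both groups, physical examination, assessment of menopausal status, breast ultrasound, and abdominal ultrasound were performed every 3 months", with yearly mammography and chest x-ray. AE assessment is not on this list.
- **Study end points:** "The primary end point of the study is to assess the adverse effects of the Capecitabine after 6 months after starting treatment". DFS and OS are timed from randomization. AEs are graded by CTCAE version 4.0; that sentence gives no arm, schedule or time origin.

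**The concern.** A between-group test of AE rates needs AEs to be looked for in the same way, over the same period, in both groups. The plan gives a schedule for one group and is silent on the other. It does not forbid recording AEs in controls, but nobody following it is told to do so.

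Two features make this matter. The trial is open label, so whether an event is asked about and noted can depend on the arm. Controls are also randomized within 4 weeks of finishing adjuvant chemotherapy, so some background AEs are plausible in both groups. If capecitabine patients are questioned more often, their recorded rate rises for that reason alone. Events never asked about in controls cannot be recovered at analysis.

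The clock has the same gap. Start of treatment, and the term treatment-emergent in the Sample size section, both refer to a date that observation patients lack. Within the capecitabine group, tying assessment to the maintenance period leaves open whether AEs are still collected to month 6 in someone who stops early.

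**Working it through.** **The plan's own figure.** The documents give 40 per group and, in the general analysis text, a two-sided alpha of 0.05. They state no power, AE rates or dropout, so the figure can be neither reproduced nor refuted. By the usual two-proportion formula without continuity correction, it fits assumed pairs such as 20% vs 50%, 30% vs 60% or 50% vs 80% at 80% power. The pair 30% vs 60% is used below.

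**AE assessments by month 6, as written**

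| | Capecitabine | Observation |
|---|---|---|
| Monthly AE assessment | 6 | 0 |
| 3-monthly examination (AEs not mentioned) | 2 | 2 |
| Start of the 6-month window | first dose | undefined |

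**Model (all assumed).** AE onsets follow a Poisson process over 26 weeks. An AE is recorded if its onset falls within a recall window of w weeks before an assessment. With true 6-month incidence p and f the share of the 26 weeks covered,

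recorded probability = 1 − (1 − p)^f.

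Six monthly assessments give f = min(1, 6w/26); two assessments at weeks 13 and 26 give f = min(1, 2w/26). Rejection rates come from exact enumeration of all 41 × 41 outcomes, using the Pearson chi-square without continuity correction at 0.05.

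*Worked case:* p = 30% in both groups, w = 4. Capecitabine: f = 24/26 = 0.92, recorded 1 − 0.7^0.92 = 28.1%. Controls: f = 8/26 = 0.31, recorded 1 − 0.7^0.31 = 10.4%. The spurious difference is 17.7 points, and P<0.05 occurs in 53% of trials.

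**Equal true incidence: share of trials with P<0.05, controls asked at months 3 and 6**

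| True incidence | 2 wk | 4 wk | 8 wk | 10 wk | 12 wk | 13 wk |
|---|---|---|---|---|---|---|
| 20% | 22% | 39% | 14% | 8% | 5% | 5% |
| 30% | 33% | 53% | 19% | 9% | 5% | 5% |
| 50% | 53% | 77% | 29% | 13% | 6% | 6% |

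The spurious recorded difference is 12–28 points at 4 weeks, 7–15 at 8, 4–9 at 10 and 0 at 13. With no recording in controls, P<0.05 occurs in 56–100% of trials.

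**If AEs persist.** If half of events are still present at the next assessment, f becomes 0.5 + 0.5f. Rejection at 2–8 week recall then falls to 7–21%. If all persist, it is nominal.

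**A simpler model.** Take full capture in the capecitabine group and a fixed share captured in controls, with 30% true risk in both. P<0.05 occurs in 4.8% of trials at full control capture, 11.7% at 75%, 36.6% at 50% and 99.9% at none.

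**A real effect, true 60% vs 30% (30 points).** Recorded difference in points:

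| Recall | Monthly vs 3-monthly | Monthly in both |
|---|---|---|
| 2 wk | 29 | 19 |
| 4 wk | 47 | 29 |
| 8 wk | 40 | 30 |
| 10 wk | 36 | 30 |
| 13 wk | 30 | 30 |

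With no control recording, the recorded difference is 57–60 points at recall of 4 weeks or more.

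**The case against.** **Monthly follow-up may be meant for everyone.** The sentence on total follow-up names no arm, and its second-year half clearly covers both groups. Read in parallel, controls would also have 6 assessments and the imbalance would vanish. But the sentence ties monthly AE follow-up to the year of taking the drug, and the AE collection sentence then names the capecitabine group. The charitable reading is possible; the plan does not state it.

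**The CTCAE sentence has no arm restriction.** True, so the fault is one of specification. But that sentence sets grading, not who is asked or when.

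**The primary end point may be descriptive.** Read within the capecitabine group, its time origin is well defined. The Aim and Sample size sections, however, require a comparison with observation, so this reading only moves the contradiction.

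**The percentages are assumed.** This stands. Results run from about 5% to 100%, and the larger figures with 3-monthly questioning assume that an AE still present at a visit is missed. With half of events persisting, the 60% vs 30% case records 30–38 points. For events rare under observation the distortion is small: with hand-foot syndrome (in the plan's words "a common adverse effect of the fluoropyrimidine chemotherapy agent capecitabine") assumed at 40% vs 0–5%, 3-monthly instead of monthly questioning of controls shifts the difference by about 3 points at most. But the primary end point is not restricted to hand-foot syndrome.

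**The time origin is a small edit.** Also true: no figure above measures it, and randomization is already the origin for DFS and OS.

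**Conclusion.** The concern holds and should be settled before enrolment. It rests on the text: the comparison that justifies the sample size has an explicit AE schedule in one group and a time origin in one group. Followed as written, ascertainment in an open-label primary comparison is unequal.

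The size of the bias cannot be fixed from the documents. It is near zero if controls' AEs are fully recalled or still present at 3-monthly visits, moderate with partial capture, and decisive if controls' AEs are not recorded. The calculations show that the gap can produce a significant result with no true difference, or overstate a real one; they do not predict what this trial will find.

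**What to change.** **Main change**
1. In Methods, add AE assessment to the assessments for both groups: the same CTCAE v4.0 form at the existing 3-monthly visits, asking about the whole interval since the previous 3-monthly visit. Do not ask about the time since the last visit, which in the capecitabine group is only one month.
2. State that the form is completed whether or not capecitabine has been stopped.
3. In Study end points, count the 6 months from randomization in both groups and define the between-group primary variable from the common month 3 and month 6 forms. Report the monthly capecitabine data descriptively.

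*Cost:* protocol wording and one form at visits already planned. Incomplete recall loses power. For an assumed true 60% vs 30%, power is 80% with full recall, 70% at 10 weeks, 62% at 8, 40% at 4 and 25% at 2. Patients questioned monthly may also recall better, so some imbalance can remain.

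**Alternative if 3-month recall is doubted.** Ask the same AE questions monthly in both groups to month 6. Power for the same case is 80% at 8-week recall, 77% at 4 and 53% at 2. This adds 4 contacts per control (months 1, 2, 4 and 5): 4 × 40 = 160 in total. It protects power better; the choice depends on whether those contacts are affordable.

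**If AEs will not be recorded in controls.** Drop the between-group test, report capecitabine-group incidence with an exact 95% confidence interval, and rewrite the aim and the sample-size basis to match.
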